Age-related degenerative disorders, such as osteoarthritis, are among the diseases with the greatest socio-economic impact; moreover, the increase in life expectancy of the population has led to an increase in the number of people affected by this disease in the last decades [Pelletier et al., 2001]. Osteoarthritis (OA) is a chronic joint degenerative disease characterized by degeneration of hyaline articular cartilage, synovial inflammation and changes in the subchondral bone. There are two forms of OA, primary and secondary; the latter occurs at a later age, tending after 60 years, and is due to the natural process of aging of the joint and / or to events of a traumatic nature. Several other etiopathogenetic factors are involved in the development of this degenerative process including genetic factors, obesity and chronic inflammatory status, and the complex pathogenesis is not yet fully determined. The joints most affected are those of the upper and especially lower limbs and the spine and the symptoms are algia, joint stiffness, muscle tension and instability, which induce the patient to immobility in an attempt to avoid pain; this symptomatology often aggravates the quality of life of elderly patients to produce a depressive state that further complicates the general clinical picture [Pelletier et al 2001; Hunziker, 2001]. The current pharmacological and physiatric treatments are not resolutive of OA and in fact, the prosthetic intervention turns out to be the only solution for the patient. In recent decades, the technology has developed more and more performing joint prostheses, inspired by different mechanical and biological principles, in order to better reproduce joint physiology and improve the efficiency of the implant. Currently the materials used have a long life span, and 90 to 95% of the operated patients have a prosthetic implant survival 10 to 15 years after surgery. However, implants can also fail for several reasons: dislocation, aseptic loosening, peri-prosthetic infections aggravated by sometimes predisposing factors of the patient, such as diabetes, which determine the need to perform a revision surgery [Pelletier et al., 2001]. In spite of this, chondrocyte has a key role in the degradation of hyaline cartilage by: i) an imbalance between its own anabolic and catabolic activity; and ii) to the reduction of the chemical-physical properties, other cellular components are more involved in the subsequent possible failure of the integration of the prosthetic implant. Modifications of the joint microenvironment, the deficiency of the regenerative response of the osteoblasts, the inappropriate activation of the chemochemical network and the activation of the synoviocytes in the inflammatory sense (activation of the pathways of NF-KB, HIF1, BMP, TGF- β , and IGF) they are all conditions and factors that can alter the osseointegrative process of a joint prosthesis [Pelletier et al 2001; Hunziker, 2001; Asahara H. et al., 2016]. The aim of the present study is to identify and evaluate the possible role of miRNAs and long non-coding RNA (lncRNA), modulated in OA, as new biomarkers useful to predict the efficiency of the osseointegration process of the prosthetic implant [Xu et al. 2016; Zhang et al. 2017; Bernard NJ. et al., 2014].

Objectives of the study

- Primary Objective

Identification and characterization of miRNAs and LncRNA, from synoviocytes, osteoblasts and chondrocytes isolated from tissue samples obtained from endo or surgery arthro-prosthesis, and related signaling involved in synoviocytes and osteoblasts cross-talk during the osteointegration process through suitable *in vitro* co-culture models [Craig I.J. et al., 2016; Lin Y. et al., 2010].

- Secondary Objectives:

Identification of other biomarkers useful for predicting the efficiency of osseointegration of the implant, through bioinformatics and molecular analysis of miRNAs, LncRNA and proteins secreted or produced by synoviocytes and osteoblasts;

Validation of data obtained on miRNAs and LncRNAs through "gain and loss of" experiments function "in primary cultures and co-cultures.

Study design

The study involves the isolation and cellular, molecular and proteomic characterization of synoviocytes, osteoblasts and chondrocytes from "waste" tissue samples obtained from patients undergoing surgery of endo or arthroplasty for osteoarthritis (Experimental Group) or interventions for other causes such as for example periarticular fracture requiring the implantation of a prosthesis (Control Group) at the Rizzoli-Sicilia Department (Bagheria-Palermo).

Deeper analysis of miRNAs and LncRNAs expressed by the synoviocytes, osteoblasts and chondrocytes will be performed in order to understand their possible involvement in the signaling of HIF1- α , β -catenin, NF-Kb and other pathways of osteogenic differentiation, through suitable experimental *in vitro* models of co-cultures. In particular, we will focus on the cross-talk between synoviocytes and osteoblasts, cell populations involved in the post-surgical articular microenvironment and on which the osteointegration process of the joint prosthesis depends.

Population

Inclusion Criteria:

- 1) Male and Female patients > 40 years old hospitalized for surgery of endo- or arthroplasty for OA (Group OA) or for surgery for joint traumatic diseases (eg femoral neck fractures) requiring the implantation of a prosthesis (Control Group);
- 2) Interval of at least three months from any previous infiltrative treatment of any kind;

3) Patients able to provide written informed consent to the study.

Exclusion Criteria

- 1) Severe cognitive defects or psychiatric disorders;
- 2) Tumor pathologies or concurrent antineoplastic therapies;
- 3) Autoimmune diseases (rheumatoid arthritis);
- 4) Surgery that involves the joint

Material and Methods

The isolated cells (synoviocytes, osteoblasts and chondrocytes) will be kept in culture under specific conditions in order to allow the isolation of proteins, mRNAs, miRNAs and lncRNAs. Cellular characterizations will be performed using FACS (Partec CyFlow Space), while the molecular characterizations will be obtained with qRT-PCR (Light-Cycler 2.0-Roche). Protein / proteomic analysis will be performed using ELISA (commercial kit), Western blot (ChemiDoc XRS + System, BIORAD) and TRIPLE TOF5600 (AB Sciex). The miRNAs and lncRNAs, identified by molecular biology techniques (qRT-PCR, LINE GENE 9640), the mRNAs and the identified proteins will be analyzed through the use of specific software, such as: TargetScanPrediction, Diana Software, MiRBase and Partec FloMax®. The miRNAs and lncRNAs that will be particularly regulated / modulated following the pathology and the reduced activation of the pathways involved in osteoblastic differentiation, will be investigated, evaluating their involvement in the regulation of HIF1- α , β -catenin, NF-Kb signaling and other possible pathways of osteogenic differentiation. Through in vitro co-culture systems (osteoblasts and synoviocytes isolated from tissues), we will evaluate the role of previously identified miRNAs and lncRNAs, in cross-talk between osteoblasts and synoviocytes isolated from patients with OA. Their role will be validated through "gain and loss of function" experiments in primary cultures and co-cultures.

Statistics

Multivariate statistical analysis of the results will be performed using R software [R Development Core Team (2008) software. A: A language and environment for statistical computing. R Foundation for Statistical Computing, Vienna, Austria. ISBN 3-900051-07-0, URL <http://www.R-project.org>.] After evaluating the normal distribution homogeneity of the variance of data the appropriate parametric statistical tests will be applied (ANOVA or GLM and Student t test) or in case of non-normality and heteroskedasticity similar non-parametric tests (eg Kruskal-Wallis and Mann-Whitney U test). The proteomics data will be analyzed by principal components analysis using MarkerViewTM 1.2.1 (SCIEX) software. The molecular interaction network between the modulated proteins that are found to be significant will be analyzed with the STRING software v10 (Search Tool for the Retrieval of Interacting Genes / Proteins; <http://string-db.org/>). The sample size was calculated using the G*Power software v.3.1.9.2 (University of Kiel, Germany), considering

a significance level $\alpha = 0.05$ and a power $1-\beta = 0.80$. For the calculation of the effect size we considered the result of variation of *ALPL* gene expression in human mesenchymal stem cells cultured in hypoxic environment (similar to the intra-articular environment) between 3 (FOI: 1.53 ± 0.34) and 7 (FOI: 2.53 ± 0.29) days and presenting an increased expression of miR-675-5p [Costa V. et al, 2017]. The effect size value $d=2.28$ was transformed into $f=1.14$, because the sample size was calculated considering a two-way ANOVA model (patient: healthy / osteoarthritis, experimental culture time: 2 short times). The maximum number of patients to be enrolled is $n=10$ of which $n=5$ osteoarthritic and $n=5$ healthy.

Enrollment Procedures

Patients considered eligible will be enrolled in the study, after providing a written informed consent.

Data Collection

Clinical data will be retrieved by patient's source document

A protocol-specific CRF reporting the results of the analyses will be provided

A CRF is required and should be completed for each included subject.

Ethics

The clinical trial protocol and its documents will be sent before initiating the study to the competent Authorities and Ethics Committees of each participating country for its approval.

The responsible investigator will ensure that this study is conducted in agreement with either the most updated Declaration of Helsinki and all the international and local laws that apply to clinical trials and to patient protection.

The protocol has been written, and the study will be conducted according to the principles of the ICH Harmonized Tripartite Guideline for Good Clinical Practice
(ref: <http://www.emea.eu.int/pdfs/human/ich/013595en.pdf>).

Informed Consent

All patients will be informed, by the investigator, of the aims of the study, the possible risks and benefits that will derive from the study participation.

The Investigator must clearly inform that the patient is free to refuse participation in the study and that can withdraw consent at any time and for any reason.

They will be informed as to the strict confidentiality of their patient data, but that their medical records may be reviewed for trial purposes by authorized individuals other than their treating physician.

The informed consent procedure must conform to the ICH guidelines on Good Clinical Practice. This implies that "the written informed consent form should be signed and personally dated by the patient or by the patient's legally acceptable representative".

The Investigator must also sign the Informed Consent form, and will keep the original at the site and a copy of the original must be handed to the patient.

The competent ethics committee for each Institution participating to the study must validate local informed consent documents before the study can be opened. It will be emphasized that the participation is voluntary and that the patient is allowed to refuse further participation in the study whenever he/she wants. This will not prejudice the patient's subsequent care.

General Principles for Human Biological Material (HBM) collection

Human biological material (HBM) collection involves the collection and storage of biological material, residual biological material or derivatives in compliance with ethical and technical requirements.

Biological material (tissue samples) will be centralized and stored at l'Istituto Ortopedico Rizzoli - Dipartimento Rizzoli-Sicilia, Bagheria (Palermo).

From here, the biological material will be used and stored according with the sample characteristic and applicable regulation.

The molecular and protein materials obtained from the isolated cells will be stored inside sterile containers (falcon, tubes, eppendorf) in the freezer at the temperature of -80 ° C at the Istituto Ortopedico Rizzoli - Dipartimento Rizzoli Sicilia.

The "Piattaforma Tecnologica per l'Ingegneria Tissutale, Teranostica ed Oncologia" laboratory will perform the research as stated in the protocol "Material and Methods" section

The following principles apply to storage of HBM:

- The Istituto Ortopedico Rizzoli will have a designated person responsible for collection and will act as a communication point
- The collected HBM should be documented, i.e. the amount remaining and its location. act as a communication point
- The storage and use of biological material will take place in accordance with the standards of good laboratory practice (GLP) and applicable legislation.

Confidentiality

In order to ensure confidentiality of clinical trial data as disposed the national and European applicable regulation, data will be only accessible for the trial Sponsor and its designees, for monitoring/auditing procedures, the Investigator and collaborators, the Ethics Committee of each corresponding site and the Health Authority.

Investigator and the Institution will allow access to data and source documentation for monitoring, auditing, Ethic Committee revision and inspections of Health Authority, but maintaining at all times subject personal data confidentiality as specified in the applicable regulation.

The Investigator must guarantee that patient anonymity is kept at all times and their identity must be protected from unauthorized persons and institutions.

All patients included in the study will be identified with a numeric code, so that no identifiable personal data will be collected.

The Investigator must have and conserve a patients' inclusion registry where it figures the personal data of the patient: name, surname, address and corresponding identification code into the study, this register will be kept on the Investigator File.

Publication policy and data ownership

The principal investigator of the study is responsible for the final report, of the publication publish all the data collected as described in the protocol and will ensure that the data are reported responsibly and consistently.

In particular, the publication of data deriving from the present study will take place independently of the results obtained.

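### Inclusion criterion 1 leaves the joint open in both groups, so with 5 v 5 donors a difference in joint mix would bias the OA-control contrast

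*Protocol*

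**What the plan says.** **Eligibility (Protocol, Population, Inclusion Criteria, item 1).** Eligible patients are those "hospitalized for surgery of endo- or arthroplasty for OA (Group OA) or for surgery for joint traumatic diseases (eg femoral neck fractures", the trauma patients being controls who need a prosthesis. No joint is named for OA donors. For controls the femoral neck is given as an example, not as a limit.

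**Study design.** The control group is described again, with an example that names no joint: "interventions for other causes such as for example periarticular fracture requiring the implantation of a prosthesis (Control Group".

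**Exclusion Criteria, item 4.** It reads "Surgery that involves the joint" and identifies no particular joint, so it does not fix the site.

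**Background.** OA is presented as a disease of several sites: "The joints most affected are those of the upper and especially lower limbs and the spine".

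**Statistics.** The sample size comes from a two-way ANOVA with patient group and culture time (two short times) as factors, f = 1.14, and "a significance level $\alpha = 0.05$ and a power $1-\beta = 0.80". The result is: "The maximum number of patients to be enrolled is $n=10$ of which $n=5$ osteoarthritic and $n=5$ healthy". The analysis text in the same section is wider. It foresees ANOVA or GLM with non-parametric alternatives, and names no covariates.

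No section requires the two groups to give tissue from the same joint, pairs donors by joint, or stratifies by it.

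**The concern.** The OA-control comparison is the step that picks out the RNAs and proteins modulated by the disease. Those candidates then go forward to the co-culture and gain- and loss-of-function work. Each donor contributes one joint, so joint of origin is a donor-level attribute, as disease group is. Further culture times or replicate cultures from the same ten donors add no information for telling the two apart.

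If the groups happen to differ in joint mix, any joint-of-origin difference in expression enters the estimated OA effect. Matching on age or sex would not remove it. If every OA donor came from one joint and every control from another, the two effects would be the same contrast.

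This belongs in the protocol because eligibility is fixed there. An analysis plan could add a joint term, but that term cannot be estimated separately from group under full alignment.

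**Working it through.** **1. The plan's own figure.** Inputs from Statistics: f = 1.14, alpha = 0.05, power 0.80, 2 x 2 cells. With numerator df = 1, denominator df = N - 4 and noncentrality f^2 x N, N = 10 gives 1.2996 x 10 = 12.996. Power is 0.779 at N = 9 and 0.849 at N = 10, so 10 is the smallest N that reaches 0.80. The stated number reproduces, taking f as given, and the point below does not change it.

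**2. Bias from unequal joint mix.** Let q_OA and q_C be the shares of donors from a given joint in each group, and D the mean difference between that joint and the other one. With additive effects:

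expected OA-control difference = OA effect + (q_OA - q_C) x D.

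The bias is zero if the mixes are alike and equals D under full alignment. If three of five OA donors and no controls come from the other joint, it is (0.6 - 0) x D = 0.6 D.

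**3. How likely is alignment?** The documents give no joint mix. Assume all five controls are hips, OA donors are independent, and a share p of them are non-hip. Full aliasing has probability p^5. Partial imbalance (one to four non-hip OA donors) has probability 1 - (1 - p)^5 - p^5.

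| p | Full aliasing | Partial imbalance |
|---|---|---|
| 0.3 | 0.0024 | 0.8319 - 0.0024 = 0.8295 |
| 0.5 | 0.0313 | 0.9688 - 0.0313 = 0.9375 |
| 0.7 | 0.1681 | 0.9976 - 0.1681 = 0.8295 |

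**4. Effect on the false-positive rate.** Simulation of a two-sided t test at 0.05, 5 v 5 donors, 200,000 runs, no true OA effect, all controls from one joint, and an assumed joint effect in SD units. This is a simplified donor-level test, not the full two-way model.

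| Assumed joint effect | 0 of 5 OA donors differ | 2 of 5 | 3 of 5 | 5 of 5 |
|---|---|---|---|---|
| 0.5 SD | 0.049 | 0.055 | 0.066 | 0.107 |
| 1 SD | 0.049 | 0.067 | 0.107 | 0.286 |
| 1.5 SD | 0.049 | 0.083 | 0.162 | 0.550 |

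As a check on the simulation, a joint effect of 2.28 SD (the plan's own d) with all five differing gives 0.883. That equals the noncentral-t power for d = 2.28 at five per group.

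**5. Could adjustment repair it?** With k of five OA donors from another joint and all controls hips, the joint-adjusted OA effect rests on the 5 - k OA hips against five control hips. Its variance is proportional to 1/(5 - k) + 1/5, against 1/5 + 1/5 = 0.4 when all donors share a joint.
- k = 3: 1/2 + 1/5 = 0.7, a standard error larger by sqrt(0.7/0.4) = 1.32.
- k = 4: 1 + 1/5 = 1.2, larger by sqrt(1.2/0.4) = 1.73.
- k = 5: no OA hip remains, and the effect cannot be estimated.

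**The case against.** **The text does not set up a knee-versus-hip comparison.** A reader might infer this from an unrestricted OA group beside a control example at the hip. The documents do not support it. The femoral neck is only an example, Study design gives a second example that names no joint, and the Protocol never mentions the knee. Both groups are equally open. This objection stands: the defect is that the criterion permits unequal mixes, not that it prescribes them.

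**A large probability is easy to misquote.** Under the assumptions of step 3, the chance of at least one non-hip OA donor is 83%, 97% and 99.8% at p = 0.3, 0.5 and 0.7. Those figures might be taken as the chance that joint and disease are inseparable, but one non-hip donor is not aliasing. The relevant figure for that is p^5.

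**The analysis is not confined to two factors.** Those factors belong to the sizing model; the analysis text would allow a joint term. This stands for a partial mix, at the loss of precision shown in step 5, but does not help under full alignment.

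**No joint effect is documented.** This also stands. No section reports a joint-of-origin effect on any miRNA, lncRNA or protein, so the error rates are a range under assumptions. With 0.5 SD and three of five donors differing, the rate is only 0.066.

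**Later experiments offer some protection.** Candidates are tested functionally in cells from OA patients, so a spurious one meets a separate hurdle. That limits the harm mainly to misdirected laboratory work in an exploratory study. It does not show whether a candidate was first selected for disease or for joint.

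**Conclusion.** The point holds as a weakness of donor selection. The eligibility criteria leave the joint open in both groups, nothing balances it, and ten donors give little room to adjust. The bias is (q_OA - q_C) x D, and full alignment could not be repaired by any analysis.

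Its size cannot be estimated from the documents. Under the stated assumptions full aliasing is the less likely outcome (0.2% to 16.8% for p from 0.3 to 0.7) and partial imbalance the more likely. For joint effects of 0.5 to 1.5 SD, the false-positive rate runs from about 0.07 to 0.16 with three of five OA donors differing, and from about 0.11 to 0.55 under full alignment.

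It would go too far to say that the study will compare different joints, or that its results are necessarily confounded: the enrolled mix may turn out alike. The change is worth making because it is cheap before enrolment, while complete alignment cannot be undone afterwards.

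**What to change.** Amend inclusion criterion 1 so that both groups give tissue from the same joint, for example the hip, which the control example already names. Specify the same harvest sites for synovium, bone and cartilage in both groups. If several joints are to be kept, which fits the Protocol's general interest in joint prostheses better, match each OA donor to a control donor of the same joint. In either case record the joint in the CRF.

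Cost: a short amendment. With one joint, the findings apply to that joint only; with matching, some available donors go unused. The documents give no case-mix figures, so the effect on recruitment time cannot be calculated, though only five donors per group are needed. N stays at 10. Because the study uses waste tissue from operations carried out for other reasons, no patient's care changes.

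### Proteins go to STRING on the strength of significance, but the method named for proteomics (PCA) yields none per protein, and no test or error criterion is tied to that selection

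*Protocol*

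**What the plan says.** All the relevant statistical text is in the Statistics section of the protocol.

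- **General tests.** Results are to be tested by ANOVA, GLM or t test, or by rank tests such as Kruskal-Wallis and Mann-Whitney if the assumptions fail.
- **Proteomics.** "The proteomics data will be analyzed by principal components analysis using MarkerViewTM 1.2.1 (SCIEX) software".
- **Next step.** "The molecular interaction network between the modulated proteins that are found to be significant will be analyzed with the STRING software v10". Neither the test nor the threshold behind that selection is given.
- **Error level and power.** These appear only in the sample-size calculation, as "a significance level $\alpha = 0.05$ and a power $1-\beta = 0.80", with an effect size taken from ALPL expression: "The effect size value $d=2.28$ was transformed into $f=1.14$, because the sample size was calculated considering a two-way ANOVA model". The factors are given as "patient: healthy / osteoarthritis, experimental culture time: 2 short times".
- **Size.** "The maximum number of patients to be enrolled is $n=10$ of which $n=5$ osteoarthritic and $n=5$ healthy".

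The search itself is wide. The primary objective reads in part "Identification and characterization of miRNAs and LncRNA, from synoviocytes, osteoblasts and chondrocytes isolated from tissue samples". The secondary objectives add proteins as possible biomarkers, and Material and Methods lists mass spectrometry (TripleTOF 5600) beside ELISA and Western blot.

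**The concern.** The two proteomics sentences do not fit together. PCA is an unsupervised summary: it can show whether samples separate and which proteins load on a component, but it does not declare a protein significant. The next sentence nevertheless uses significance as the entry condition for the network analysis. An analyst must supply the missing step, and different choices give different protein lists and different networks.

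The only error level at hand is the 0.05 from the sizing text, so it is the natural default. It was chosen for one endpoint. In a screen of many proteins it admits chance findings in proportion to the number tested, and STRING would then draw a network that includes them. The functional experiments are described for miRNAs and lncRNAs only, so no such follow-up is stated for the protein list.

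The stated power has the same limit. It describes one test, not a search over many features.

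**Working it through.** **Inputs from the Statistics section:** d = 2.28, f = 1.14, alpha = 0.05, power = 0.80, two-way ANOVA with 2 × 2 cells, and 5 + 5 patients. The effect size is used as stated.

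**Assumed, because the protocol does not give them:** the number of proteins tested (m = 10, 100, 1000) and the share π that truly differ (5%, 10%, 20%). Also assumed are that d = 2.28 applies to every true difference and, for the chance of at least one false positive, that tests are independent.

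**1. The plan's own figure.** f = d/2 = 2.28/2 = 1.14. The noncentral F has numerator df 1, denominator df N − 4 and noncentrality f² × N.
- N = 9 gives power 0.779.
- N = 10 (noncentrality 1.2996 × 10 = 13.0) gives power 0.849.

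The smallest N reaching 0.80 is 10, so the stated size reproduces for one endpoint at one alpha of 0.05.

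**2. False positives if 0.05 were used per protein and all were null.** Expected number = 0.05 × m; chance of at least one = 1 − 0.95^m.

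| m (assumed) | Expected | At least one |
|---|---|---|
| 10 | 0.5 | 40% |
| 100 | 5 | 99.4% |
| 1000 | 50 | about 100% |

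These figures are for one screen, for example one cell type.

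**3. False share of the hit list.** A two-sided t test with 5 versus 5 at d = 2.28 has noncentrality 2.28 × √(5/2) = 3.605 on 8 df, and power 0.883. False share = 0.05(1 − π) / [0.05(1 − π) + 0.883π].
- π = 20%: 0.0400 / (0.0400 + 0.1766) = 18%
- π = 10%: 0.0450 / (0.0450 + 0.0883) = 34%
- π = 5%: 0.0475 / (0.0475 + 0.0441) = 52%

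**4. Whether the stated power carries over to a screen.** In the protocol's own two-way model at N = 10, power is 0.849 for one test. It is 0.376 at 0.05/10 and 0.084 at 0.05/100. These Bonferroni levels are an illustration; false discovery rate control is less strict, and its cost depends on the unknown share of true signals.

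**5. Whether the rank test can serve the screen.** With 5 versus 5 the smallest exact two-sided Mann-Whitney p is 2/C(10,5) = 2/252 = 0.0079. Benjamini-Hochberg at 10% over 100 proteins needs k × 0.10/100 ≥ 0.0079, so k ≥ 7.9. At least 8 proteins must sit at that floor before any can be declared at that p-value. A shorter list of true findings could not be declared at all.

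**The case against.** The strongest reply is that the general tests cover the results as a whole and nothing excludes proteins. An analyst could test each protein and use PCA as the multivariate step. This stands in part: the selection is not impossible to carry out, and PCA is the only method named in the proteomics sentence, not in the whole section. What it leaves open is which test and which criterion define significance for the list sent to STRING.

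A second reply is that multiplicity control in exploratory omics work is commonly left to a statistical analysis plan, which is not shown here. That also stands, and the absence of an adjustment method is not by itself the point. The point is that the protocol's own text joins a method to a selection which that method cannot make.

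Three stronger readings are tempting and are not supported:

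- **That the protocol prescribes an unadjusted screen at 0.05.** It does not. The level appears only as a sample-size input, and the text is silent on adjustment.
- **That this selection also governs the gain- and loss-of-function experiments.** The significance condition is written for proteins entering STRING. The miRNAs and lncRNAs are chosen, under Material and Methods, by their modulation with the disease and with reduced osteogenic pathway activation, and they then undergo experimental validation.
- **That the list will contain many false positives.** This depends on the number of proteins and the share of true signals, and neither is given. With 10 null proteins the expected count is half of one.

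**Conclusion.** The point holds in a limited form. The PCA-to-STRING route lacks the step that makes a protein significant, and the 0.05 and 0.80 in the protocol belong to a single-gene calculation, not to a multi-feature screen.

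If the gap were filled by the general tests at 0.05, between about one hit in six and one in two would be false. That range is for 20% down to 5% of proteins truly different, all at d = 2.28. That effect came from a change over culture time in one gene in mesenchymal stem cells, so its use for protein differences between patient groups is a further assumption. The sample size itself reproduces and is not in dispute here.

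This should be corrected before the proteomics data are analysed. It is more than a wording slip, because the list that reaches STRING depends on it.

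**What to change.** In the Statistics section:

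1. Keep PCA, described as a descriptive or quality check.
2. Name a per-protein comparison of the two groups on the log scale. A variance-moderated t test suits 5 versus 5; the rank test does not, for the reason in step 5 of the working.
3. Apply Benjamini-Hochberg control at a level stated in advance (10% is reasonable for a discovery screen), within each assay and cell type, and send only that list to STRING.
4. Report other proteins with raw p < 0.05 as exploratory, labelled as such.
5. State that alpha 0.05 and power 0.80 apply only to the single endpoint used for sizing.

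If a statistical analysis plan already fixes items 2 to 4, a cross-reference would do.

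The cost is a few sentences and a few lines of R, with no extra patients or assays. The downside is a shorter primary protein list and a narrower power statement.

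### Does the sample size lack a basis because its only effect size is a culture-time change, not an osteoarthritis-versus-control difference?

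*Protocol*

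**What the plan says.** The sample size is given in the Protocol, Statistics, with alpha 0.05 and power 0.80.

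- **Source of the effect size:** "For the calculation of the effect size we considered the result of variation of *ALPL* gene expression in human mesenchymal stem cells" kept in hypoxia. The contrast is "between 3 (FOI: 1.53 ± 0.34) and 7 (FOI: 2.53 ± 0.29) days and presenting an increased expression of miR-675-5p". It is a change over culture time, with no osteoarthritis or healthy group in it.
- **Reason for the source:** the hypoxic culture is described as resembling conditions inside the joint.
- **Model:** d = 2.28 is converted to f = 1.14, "considering a two-way ANOVA model (patient: healthy / osteoarthritis, experimental culture time: 2 short times").
- **Result:** at most 10 patients, "of which $n=5$ osteoarthritic and $n=5$ healthy".

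The section does not say whether the 0.80 refers to the patient factor, the culture-time factor or their interaction. The Protocol gives no expected osteoarthritis-versus-control difference and no between-patient SD.

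**The concern.** The calculation fixes the numbers by disease group, and its 0.80 is the only stated justification for 5 versus 5. The input, however, describes how one gene changes between two culture days in mesenchymal stem cells. A within-culture change says little about how far osteoarthritic and control patients differ, or how much patients vary within a group.

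The group comparison also has a use later on. Material and Methods follows up "The miRNAs and lncRNAs that will be particularly regulated / modulated following the pathology". If the 0.80 is read as the power of that comparison, it rests on a borrowed effect with no argument for the transfer. If it is read as the power for culture time, the input fits in kind but 5 versus 5 has no stated power basis. On either reading, a reader facing a null group result could not tell how informative it is.

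**Working it through.** **Inputs from the Protocol, Statistics:** alpha 0.05; power 0.80; d = 2.28; f = 1.14; two factors with two levels each; 10 patients, 5 per group. I take d as stated.

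**1. Reproducing N = 10.** The software options are not given, so I use the fixed-effects F test with four cells: numerator df 1, denominator df N − 4, noncentrality f² × N.

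- f = 2.28 / 2 = 1.14; f² = 1.2996.
- N = 9: noncentrality 11.70, df 1 and 5, power 0.779.
- N = 10: noncentrality 13.00, df 1 and 6, power 0.849.

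N = 10 is the smallest total that reaches 0.80. This treats the 10 as independent observations spread over four cells (2.5 per cell).

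**2. Does it matter which term was meant?** Numerator df are 2 − 1 = 1 for patient, 2 − 1 = 1 for time, and 1 × 1 = 1 for the interaction. With f = 1.14 the calculation in step 1 is the same for all three, so naming the term does not move N.

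**3. Group contrast if 2.28 SD held between groups.**

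- One culture time, two-sample t test, 5 versus 5, df 8: noncentrality 2.28 × √(5/2) = 3.605, power 0.883.
- Both times averaged per patient: the SD of the mean is SD × √((1 + ρ)/2), where ρ is the within-patient correlation. The Protocol gives no ρ, so 0, 0.5 and 0.8 are assumed. Power is 0.993, 0.952 and 0.913.

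All of these exceed 0.80.

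**4. Smallest group difference with 80% power.**

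| Analysis | Difference (SD) |
|---|---|
| t test, one time | 2.02 |
| Both times averaged, ρ = 0 | 2.02 × √0.50 = 1.43 |
| Both times averaged, ρ = 0.5 | 2.02 × √0.75 = 1.75 |
| Both times averaged, ρ = 0.8 | 2.02 × √0.90 = 1.92 |
| Four-cell ANOVA, N = 10 | 2.13 |

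**5. Smaller differences (assumed; none is in the Protocol).**

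| True difference | One time | Averaged, ρ = 0 / 0.5 / 0.8 |
|---|---|---|
| 1.0 SD | 0.286 | 0.502 / 0.363 / 0.312 |
| 1.5 SD | 0.549 | 0.835 / 0.671 / 0.593 |

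Power can therefore fall well short of 0.80, but only on values the document neither states nor implies.

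**Side check on d.** The quoted means and SDs with the usual pooled SD give 1.00 / √((0.34² + 0.29²)/2) = 1.00 / 0.316 = 3.16, not 2.28. That is a separate matter. Here the stated d is the smaller of the two, and f = 1.58 would give power 0.984 at N = 10 in the four-cell ANOVA, so it does not undermine N = 10.

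**The case for a change.** The strongest case for a change is that a formal power figure should say what it powers. The study has an experimental and a control group, the numbers are fixed by group, and the Protocol's publication policy commits to publishing whatever is found. The hypoxia argument supports the cell model; it does not support treating a day 3 to day 7 change as a disease difference. Rewording one paragraph would cost no patients, assays or analyses.

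The factual part of this stands. The ANOVA term is not named, the effect is a surrogate, and nothing in the document supports 0.80 specifically for osteoarthritis versus control.

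The step from there to a required change is weaker:

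- The Protocol does not attach the 0.80 to the group comparison. A time contrast is the same kind of effect as the culture-time factor in the stated model.
- The primary objective is to identify and characterise RNAs and their signalling in co-culture. No osteoarthritis-versus-control hypothesis is set, and no significance test is named as the rule for choosing RNAs to follow up.
- The surrogate, its values and the reason for it are disclosed, so a reader can discount the figure.
- A replacement statement brings its own choices. The detectable difference depends on the test (about 2.0 SD for a t test at one time, about 2.1 SD for the four-cell ANOVA), and calling the group comparison exploratory would give it a status that the Protocol does not.

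**Conclusion.** The concern does not call for a change. It correctly describes an unnamed ANOVA term and a borrowed effect size whose transfer to the disease factor is not argued. It does not show a wrong figure: N = 10 follows from f = 1.14 whichever term was meant (0.849 at 10, 0.779 at 9), and the borrowed effect gives 0.88 to 0.99 for the group contrast. The low values, such as 0.29 at 1.0 SD, rest on an assumed difference and are not evidence that the study is underpowered.

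In a laboratory study of at most 10 patients, a disclosed surrogate effect is an acceptable planning choice, and clearer wording would leave the sample size, the analyses and the results as they are. This conclusion takes d = 2.28 as stated, a two-sided 0.05 test of one marker, and within-patient correlations of 0 to 0.8. It does not establish that power for osteoarthritis versus control is 0.80. Whoever interprets that comparison should bear in mind that, for one marker, 5 versus 5 reaches 80% power only for differences of about 1.4 to 2.1 SD or more, depending on the analysis.
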